7 PLANNED ANALYSIS

For End-Of-Treatment (EoT) tables, the set of summary statistics is: N / Mean / SD / Min / Median / Max..

For tables that are provided for endpoints with some extreme data, median, quartiles and percentiles should be preferred to mean, standard deviation, minimum and maximum.

Tabulations of frequencies for categorical data will include all possible categories and will display the number of observations in a category as well as the percentage (%) relative to the respective treatment group (unless otherwise specified, all patients in the respective patient set whether they have non-missing values or not). Percentages will be rounded to one decimal place. The category missing will be displayed only if there are actually missing values.

7.1 DEMOGRAPHICS AND OTHER BASELINE CHARACTERISTICS

Only descriptive statistics are planned for this section of the report.

7.2 CONCOMITANT DISEASES AND MEDICATION

Only descriptive statistics are planned for this section of the report.

A summary of concomitant diseases will be provided by treatment group, System Organ Class (SOC) and Preferred Term (PT).

7.3 TREATMENT COMPLIANCE

Only descriptive statistics are planned for this section of the report.

Overall compliance will be calculated as mentioned in CTP section 4.3

7.4 PRIMARY ENDPOINT

The primary analysis is at 12 weeks and will be performed on the full analysis set (FAS).

Figures and tables will be displayed for the MMRM analysis results over time.

7.4.1 Primary efficacy analysis

The primary analysis and hypothesis testing are described in section 7.3.1 of the CTP.

Proprietary confidential information © 2017 Boehringer Ingelheim International GmbH or one or more of its affiliated companies

7.5 SECONDARY ENDPOINTS

Figures and tables will be displayed for the MMRM and ANCOVA analyses results over time.

7.5.1 Key secondary endpoint

This section is not applicable as no key secondary endpoint has been specified in the protocol.

7.5.2 Other Secondary endpoints

The same primary analysis model will be performed for the secondary endpoint CDR-SB.

The secondary endpoints ADAS-Cog11 and ADCS-ADL-MCI will use the following model:

ANCOVA:

Analysis of covariance will be used for the change from baseline secondary endpoint score after 12 weeks of treatment; terms include baseline value for secondary endpoint measure and treatment.

[REDACTED]

[REDACTED]

[REDACTED]

[REDACTED]

Proprietary confidential information © 2017 Boehringer Ingelheim International GmbH or one or more of its affiliated companies

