### 6.2.1 Screening and run-in period(s)

#### Visit 1 (screening)

- No trial procedures should be done unless the patient and study partner have consented to taking part in the trial.
- Once the patient has consented, the patient is considered to be enrolled in the trial and has started screening. The patient should be recorded on the enrolment log and be registered in the IRT as a screened patient.
- Informed consent for optional pharmacogenomics sampling, if applicable should be obtained.
- For diabetic patients with antidiabetic therapy: exclusion of hypoglycemia for the period of the neuropsychological assessment (documented plasma glucose concentration  $\geq 90$  mg/dl (5mmol/l) at the beginning and directly after the assessment). If glucose is too low patients need to eat a snack and then be retested to confirm that the blood sugar value is above 90 mg/dl before the tests are started
- The following screening procedures must however be performed in the order of the [Flow Chart](#): MMSE, FCSRT, (Wechsler Memory Visual Paired Associates test, if applicable), CDR, ADAS-cog11, MRI/CCT and PET/ CSF sampling (whichever applicable) to ensure that undesirable, invasive screening procedures are deferred until necessary.
- If the patient fails screening due to the results of the MMSE and/or the CDR then an alternative participation in study 1289.7 might be considered, where applicable.
- Administration of C-SSRS (baseline/screening scale)
- Collection of urine and blood for safety laboratory testing including testing for HIV, Syphilis and vitamin B12 and folate levels.
- Collection of blood samples for optional soluble biomarker evaluation from patients who consent.
- If patient does not meet inclusion/exclusion criteria at visit 1 then the patient must be recorded in IRT and CRFs as a screen failure.
- If the patient is eligible according to inclusion/exclusion criteria available at visit 1, the run-in visit (visit 2) should be scheduled. Patient should be reminded to come for visit 2 in the morning.
- Patients are allowed to have a light breakfast/ meal before coming to the study site.
- Patients should be reminded not to take occasionally used sleeping aids (see [section 4.2.2.1](#)) in the evening prior to visit 2.
- Patient should be reminded to inform the study site in case of adverse events.

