### 7.2 NULL AND ALTERNATIVE HYPOTHESES

The objective of this exploratory trial is to demonstrate proof-of-concept and also explore the dose response of BI 409306 in NTB total score change from baseline (Visit 3) after 12 weeks treatment. The hypotheses testing will be carried in the following steps. No multiplicity adjustment will be made; hence all the p-values will be descriptive. All tests will be tested at a two-sided alpha 0.05.

- Step 1 for Proof-of-Concept:

$H_{1-0}$ : Mean NTB response of pooled doses of 10 mg QD, 25 mg QD, 25 mg BID and 50 mg QD = Mean NTB response of placebo

$H_{1-a}$  : Mean NTB response for pooled doses of 10 mg QD, 25 mg QD, 25 mg BID and 50 mg QD  $\neq$  Mean NTB response of placebo

If the null hypothesis  $H_{1-0}$  is rejected in favour of  $H_{1-a}$ , then the proof of concept is established.

- Step 2 for dose response finding:

A regression model will be fitted first as the following functional form.

$$\mu(d_i) = \beta_0 + \beta_1 d_i + \beta_2 d_i^2,$$

where  $\mu(d_i)$  denotes the mean response of NTB of the dose level  $i$  group,  $d_i$  denotes for dose levels  $i$ , for  $i = 1, 2, \dots, 5$  and  $\beta$ 's are the coefficients. The dose  $d_i$  will be treated as continuous variable.

Testing for linear dose response curve

$$H_{2-0}: \beta_1 = 0, \beta_2 = 0$$

$$H_{2-a}: \beta_1 \neq 0, \beta_2 = 0$$

If the null hypothesis  $H_{2-0}$  is rejected in favour of  $H_{2-a}$ , then the following test will be tested for quadratic dose response curve.

$$H_{3-0}: \beta_2 = 0$$

$$H_{3-a}: \beta_2 \neq 0$$

- Step 3:

Once the dose response curve is determined from Step 2, the dose group with peak response in the selected model will be tested as follows:

$H_{4-0}$ : The dose group with peak response in the respective model Mean NTB response = Mean NTB response of placebo.

$H_{4-a}$ : The dose group with peak response in the respective model Mean NTB response  $\neq$  Mean NTB response of placebo.

In addition to the 3 steps above, the confidence intervals of difference in treatment effect against placebo will be presented for efficacy evaluation.

Note Step 1 and Step 3 the testing will be based on the adjusted means of NTB response from the primary model as described in [section 7.3](#)

For the secondary endpoint, all calculated p-values should be considered as descriptive for the analysis of secondary endpoint. Therefore, no alpha correction will be carried out.

Proprietary confidential information.

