#### 7.6 DETERMINATION OF SAMPLE SIZE

The primary efficacy hypothesis will be tested by comparing the dose group of BI 409306 with the peak response in the fitted regression model to the placebo group on the primary

Proprietary confidential information.

© 2017 Boehringer Ingelheim International GmbH or one or more of its affiliated companies. All rights reserved.

This document may not - in full or in part - be passed on, reproduced, published or otherwise used without prior written permission.

endpoint, the change from baseline in NTB total score after 12-week treatment. (See [section 7.2](#) for the details of hypothesis testing.)

As previously mentioned, the randomization allocation ratio of 1:1:1:1:2 of 10 mg, 25 mg, 50 mg, 25 mg BID of BI 409306, and placebo is used so that 33 % of patients will be randomized to placebo. Since these results in an unequal allocation of treatment to placebo, the sample size required for the active treatment and placebo for various effect size are displayed separately. The sample size calculations in [Table 7.6:1](#) displays the range of effect sizes considered for this trial under these assumptions using a 2-sided alpha of 0.05 with 80 % power. The two-sample t-test method with unequal n's in nQuery Advisor 6.01 was used for the calculation.

Table 7.6: 1 Sample size calculations

Standardized effect size	0.45	0.50	0.55	0.6	0.65
Power	80%	80%	80%	80%	80%
n for each active treatment arm	59	48	40	34	29
n for placebo arm	118	96	80	68	58
Total	354	288	240	204	174

Based on the calculations provided in [Table 7.6:1](#), a sample size of 48 per active treatment arm and 96 for placebo arm was selected as adequate for a phase II proof of concept trial. This sample size would allow us to detect an effect size of 0.5 with 80 % power or an effect size of 0.6 with 92 % power, 2-sided alpha at 0.05.

*Assuming a 10% dropout rate, this sample size would allow us to detect an effect size of 0.53 with 80% power and assuming a 20% dropout rate, this sample size would allow us to detect an effect size of 0.56 with 80% power, 2-sided alpha at 0.05.*

Proprietary confidential information.

© 2017 Boehringer Ingelheim International GmbH or one or more of its affiliated companies. All rights reserved.  
This document may not - in full or in part - be passed on, reproduced, published or otherwise used without prior written permission.

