6.7 BASELINE, TIME WINDOWS, AND CALCULATED VISITS

For efficacy, the baseline is defined as the pre-treatment observation at Visit 3. All other baseline variables will be observed from Visit 1.

For laboratory safety measurements, the last values prior to study drug administration will be considered as baseline values.

The midpoint between two on-treatment visits defines the end of a time window, with the midpoint being included in the time window of the preceding visit.

Table 6.7: 1 Time windows for all pre/on-treatment safety visits

Visit number	Visit label	Planned days	Interval (actual days on treatment)
1	Screening	-28	(-∞, PBORI-1]
2	Placebo Run-in period	-14	[PBORI ,TREATMENT-1]
3	Baseline	1	[NA, 1]
4a	Week 1	8	[2, 11]
4b	Week 2	15	[12, 18]
4c	Week 3	22	[19, 25]
5	Week 4	29	[26, 43]
6	Week 8	57	[44, 73]
EOT	Week 12	85	[74, 99]
FU	Follow-up	113	[100, Study drug stop date + 7 days]

These time windows are defined based on the planned number of days after the date of first administration of study drug. Reasons to base the time windows on the actual treatment start date rather than the randomization date are:

- If first intake of study drug shows a large delay by e.g. more than one week after the date of randomization, a measurement taken four weeks after randomization rather reflects the drug effect after three weeks than after four weeks and thus may underestimate the treatment effect at this visit.
- With large delays of the introduction of study drug after the randomization, the time window for the first on-treatment visit could include times the patient was not yet on study drug.

Proprietary confidential information © 2017 Boehringer Ingelheim International GmbH or one or more of its affiliated companies

Table 6.7: 2

Time windows for on-treatment efficacy measurement scheduled for each on treatment visit

Visit Number	Visit label	Planned days	Time window (actual days on treatment)	
			Start	End ^A
3	Baseline	1	NA	1 ^B
5	Week 4	29	2	57
EOT	Week 12	85	58	Study drug stop date + 7 days

A In case of premature discontinuation of the study drug an EOT Visit has to be performed. If such an EOT Visit falls into the time window of a previous visit, measurements will be assigned to this previous visit and the visit value will be determined as described below. In this case the time window for the visit that includes EOT Visit will end 7 days after the study drug stop date, including Day 7.

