9.3 SAS CODE

The below table summarizes the SAS code for the main analyses

Table 9.3.1 SAS Code for main analyses

Analysis	Code	Comments
Dose response	
Test the following model:
 $\mu(d_i) = \beta_0 + \beta_1 d_i + \beta_2 d_i^2$ 
PROC GLM DATA=one;
 
MODEL chgept = trt trt*trt;
 
RUN;
 
Treat BID dose as an in between dose = (QD + 2*QD)/2
	
Dose is treated as a continuous variable.
 
$\mu(d_i)$ denotes the mean response of dose level i.

MMRM	
PROC MIXED DATA=dat cl method=reml ORDER=formatted;
 
CLASS trt visit patient ;
 
MODEL chgept = trt baseline visit trt*visit baseline
 
/ ddfm=KR solution;
 
REPEATED visit / type=un subject=patient r rcorr ;
 
LSMEANS trt*visit / pdiff=all cl;
 
RUN ;
	
ANCOVA	
PROC MIXED data=one METHOD=reml ORDER=formatted;
 
CLASS trt ;
 
MODEL chgept = baseline trt ;
 
LSMEANS trt / CL DIFF OM ;
 
RUN;
	

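### ADAS-Cog11 is scored twice before treatment, but its readable ANCOVA adjusts only for the Visit 3 score; adding the Visit 1 score is an optional gain in precision

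*SAP*

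**What the plan says.** Protocol 6.2.1 lists the tests to be done in order at Visit 1: "MMSE, FCSRT, (Wechsler Memory Visual Paired Associates test, if applicable), CDR, ADAS-cog 11". Protocol 6.2.2 and the Flow Chart schedule ADAS-Cog11 again at Visit 3 and at end of treatment. Each patient who reaches randomisation should therefore have two pre-treatment ADAS-Cog11 scores. The inclusion criteria in Protocol 3.3.2 rest on MMSE, global CDR, FCSRT or the Wechsler back-up test, and biomarkers. ADAS-Cog11 is not among them.

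SAP 6.7 settles which score counts: "For efficacy, the baseline is defined as the pre-treatment observation at Visit 3". SAP 7.5.2 gives the ANCOVA for ADAS-Cog11 and ADCS-MCI-ADL one baseline term and treatment: "terms include baseline value for secondary endpoint measure and treatment". The code in SAP 9.3 agrees: "MODEL chgept = baseline trt". CDR-SB has a different model, the MMRM used for the primary endpoint. Protocol 7.2 makes all secondary p-values descriptive, and Protocol 7.3.2 promises adjusted means and contrasts with 95% confidence intervals.

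**The concern.** A single cognitive score carries test-retest noise. A second pre-randomisation reading of the same scale usually helps to predict the week 12 score. Using it as a covariate cannot bias a randomised comparison. The readable plan collects that reading for ADAS-Cog11 and then gives it no analysis role.

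What is at stake is interval width. The secondary p-values are descriptive, so the ADAS-Cog11 result will be read from its estimates and confidence intervals, with 48 patients planned per active arm. Patients already sit the Visit 1 test, so any gain needs no further assessment.

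**Working it through.** **1. The plan's own figure.** Inputs from Protocol 7.2 and 7.6: "All tests will be tested at a two-sided alpha 0.05"; "using a 2-sided alpha of 0.05 with 80 % power"; "a sample size of 48 per active treatment arm and 96 for placebo arm was selected". The method is a two-sample t-test with unequal group sizes and no covariate. At effect size 0.5 the noncentrality is 0.5/√(1/48 + 1/96) = 0.5/0.1768 = 2.83 on 142 degrees of freedom, which gives 80.2% power. At 0.6 it is 3.39, which gives 92.1%. This matches the stated "an effect size of 0.5 with 80 % power or an effect size of 0.6 with 92 % power", and the same calculation returns every column of Table 7.6:1. These figures concern NTB. The plan gives no power for ADAS-Cog11.

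**2. Formula.** ANCOVA of change with baseline as covariate estimates the same treatment effect as ANCOVA of the week 12 score, so the residual variance of the week 12 score is what counts. Let a be the correlation of Visit 1 with Visit 3, b that of Visit 3 with week 12, and c that of Visit 1 with week 12. With Visit 3 alone the residual variance is 1 − b² (in units of the score variance). Adding Visit 1 cuts it by the fraction

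(c − ab)² / [(1 − a²)(1 − b²)].

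**3. Results.** The documents give none of these correlations; all values below are assumptions.

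| a | b | c | Cut in residual variance | Standard error ratio |
|---|---|---|---|---|
| 0.70 | 0.70 | 0.70 | 0.0441/0.2601 = 17.0% | 0.911 |
| 0.80 | 0.80 | 0.80 | 0.0256/0.1296 = 19.8% | 0.896 |
| 0.90 | 0.90 | 0.90 | 0.0081/0.0361 = 22.4% | 0.881 |
| 0.80 | 0.80 | 0.75 | 0.0121/0.1296 = 9.3% | 0.952 |
| 0.85 | 0.85 | 0.80 | 0.0060/0.0770 = 7.8% | 0.960 |
| 0.85 | 0.80 | 0.75 | 0.0049/0.0999 = 4.9% | 0.975 |
| 0.80 | 0.80 | 0.70 | 0.0036/0.1296 = 2.8% | 0.986 |
| 0.90 | 0.85 | 0.80 | 0.0012/0.0527 = 2.3% | 0.988 |
| any | any | a × b (pure AR(1)) | 0% | 1 |

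**4. Decay combined with measurement error.** The Flow Chart allows 1-35 days of screening and 14-21 days of run-in, so Visits 1 and 3 lie about 15 to 56 days (2 to 8 weeks) apart, against 12 weeks from Visit 3 to end of treatment. Take the correlation at t weeks as λ(r/λ)^(t/12), with reliability λ of 0.85-0.95, 12-week correlation r of 0.6-0.9 (below λ) and a gap of 2.3-8 weeks. The cut then runs from 0.1% (r 0.6, λ 0.95, gap 8) to 13.3% (r 0.8, λ 0.85, gap 2.3).

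**5. Cost.** With all 288 patients, five arms and one covariate, 288 − 6 = 282 residual degrees of freedom become 281, a loss of about 1/282 = 0.35%.

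**The case against.** The strongest reply is that nothing is wrong. ANCOVA on one pre-specified pre-treatment baseline is valid and unbiased, Visit 3 is used as baseline consistently, and the endpoint is secondary and descriptive. That stands, and it makes this an optional improvement.

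The equal-correlation rows are also the most favourable. They need two readings 2 to 8 weeks apart to correlate no better than two readings 12 weeks apart. In the two rows where the shorter gap has the higher correlation, the cut is 4.9% and 2.3%. Protocol 3.2 describes a run-in that familiarises patients with the test setting, and Protocol 3.3 acknowledges learning effects for MMSE and CDR. A first-exposure score may therefore predict week 12 less well. A separate covariate absorbs a shift in the mean, but a weaker correlation would lower the gain. Against this, exactly zero gain under AR(1) decay requires a test without measurement error, which is unlikely for a cognitive scale.

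A reader might infer more than the documents support:

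- **That the Visit 1 score is discarded.** Text after the ANCOVA in SAP 7.5.2 is blacked out. Only the readable models can be said not to use it.
- **That CDR-SB has the same unused baseline.** The Flow Chart schedules CDR at screening and CDR-SB from Visit 3. The screening CDR serves eligibility as a global score of 0 or 0.5, which would also restrict the range of any box sum. Nothing says that Visit 1 box scores are recorded.
- **That the NTB model should take in ADAS-Cog11.** NTB is not given at Visit 1, so no second NTB baseline exists. This would put a different scale into the protocol-specified primary model. With assumed correlations of 0.90 (NTB with NTB) and 0.60 (NTB with ADAS-Cog11), the cut is (0.60 − 0.54)²/(0.19 × 0.64) = 3.0%.
- **That power would rise from 80% to 87-89%.** That is the equal-correlation arithmetic applied to a power planned for NTB.

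**Conclusion.** The point holds for ADAS-Cog11 alone. Two pre-treatment scores are scheduled, and the readable ANCOVA adjusts for one. Adding the Visit 1 score would probably narrow the intervals, by an amount the documents cannot settle. Residual variance falls by about 2-9% in the fading-correlation cases (standard error down about 1-5%) and by 17-22% with equal correlations of 0.7-0.9 (standard error down about 9-12%). There is no gain under pure AR(1) decay. Every one of these figures rests on assumed correlations. Because the possible loss is one degree of freedom, the trade favours the change, but leaving the model as it stands would not make the analysis wrong. The primary NTB analysis, the ADCS-MCI-ADL model (which has no Visit 1 score) and the sample size of 288 are unaffected.

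**What to change.** Before unblinding, amend SAP 7.5.2 and 9.3 for ADAS-Cog11 only:

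- Keep change from the Visit 3 baseline as the endpoint.
- Add the Visit 1 score as a second covariate: `MODEL chgept = baseline screen trt`. Do not average the two visits into the baseline of the change score, because a practice shift between them would then enter the endpoint.
- Where Visit 1 is missing, fill the covariate from pre-treatment data only, for example the Visit 3 score, so that no patient is dropped. The amendment log shows that ADAS-Cog11 joined the listed screening procedures with Amendment 1, so anyone screened before then may lack it.
- Add Visit 1 CDR-SB and its visit interaction to the CDR-SB MMRM only if Visit 1 box scores turn out to be in the database.

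If the sponsor prefers Visit 3 alone, one sentence on why ADAS-Cog11 is collected at Visit 1 would close the point. The cost is a short SAP revision, one degree of freedom and the fill rule, with no new assessments.

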7.7 EXTENT OF EXPOSURE

Extent of exposure will be calculated as the difference between last intake of study drug and the first administration of the study drug plus one day. Cumulative exposure will be displayed by >=weeks displayed in the CTP flowchart.

7.8 SAFETY ANALYSIS

All safety analyses will be performed on the treated set.

Analysis will be performed as defined in Section 7.3.3 of the CTP.

7.8.1 Adverse events

7.8.1.1 Assignment of AEs to treatment

Unless otherwise specified, the analyses of adverse events will be descriptive in nature. All analyses of AEs will be based on the number of patients with AEs and NOT on the number of AEs.

For analysis multiple AE occurrence data on the CRF will be collapsed into an AE event provided that all of the following applies:

All AE attributes are identical (LLT, intensity, action taken, therapy required, seriousness, reason for seriousness, relationship, outcome).

The occurrences were time-overlapping or time-adjacent (time-adjacency of 2 occurrences is given if the second occurrence started on the same day or on the day after the end of the first occurrence)

For further details on summarization of AE data, please refer to [\(2, 3\)](#)

The analysis of adverse events will be based on the concept of treatment emergent adverse events. That means that all adverse events occurring between first drug intake till last drug intake + residual effect period will be assigned to the randomized treatment. All adverse events occurring before first drug intake will be assigned to 'screening' and all adverse events occurring after the residual effect period will be assigned to 'post-treatment' (for listings only). For details on the treatment definition, see [section 6.1](#).

7.8.1.2 Analysis of other significant AEs

According to ICH E3 (11), AEs classified as 'other significant' needs to be reported and will include those non-serious and non-significant adverse events with

- (i) 'action taken = discontinuation' or 'action taken = reduced', or
- (ii) marked haematological and other lab abnormalities or lead to significant concomitant therapy as identified by the Clinical Monitor/Investigator at a Medical Quality Review Meeting.

Proprietary confidential information © 2017 Boehringer Ingelheim International GmbH or one or more of its affiliated companies

7.8.1.3 AE summaries

An overall summary of adverse events will be presented.

The frequency of patients with adverse events will be summarized by treatment, primary system organ class and preferred term (mention MedDRA levels to be displayed in the tables). Separate tables will be provided for patients with other significant adverse events according to ICH E3 ([4](#)), for patients with significant non-serious adverse events (only if these are defined for the project) and for patients with serious adverse events, for patients with AEs leading to discontinuation, and for patients with drug-related AEs.

The system organ classes will be sorted by default alphabetically, preferred terms will be sorted by frequency (within system organ class).

